[name] – Research Proposal

A Patient-oriented risk communication tool to improve patient experience, knowledge and outcomes after elective surgery

A Patient-oriented risk communication tool to improve patient experience, knowledge and outcomes after elective surgery

NCT Number: NCT03422133

[name] – Research Proposal

A Patient-oriented risk communication tool to improve patient experience, knowledge and outcomes after elective surgery

Background

Patients consistently report wanting more information about their expected outcomes after surgery; when patients have greater knowledge about surgery they are less anxious and more satisfied. However, most patients report being poorly informed about what to expect after surgery (such as how their risk of complications, or how long they will be in hospital). Our team has reviewed over 240 preoperative consultations for surgery patients at TOH, and in only 19% was there any documentation of a patient's personalized risks. Furthermore, even in cases where documentation was present, patients were provided with qualitative summaries, which are typically meaningless to patients. Following major surgery, 40% of patients experience at least one adverse event, and at TOH, 15% of patients experience a serious complication. Therefore, patients at TOH are undergoing surgery with the hope of experiencing a positive health outcome, but without clear, timely and engaged communication of the risks inherent in having surgery. This lack of communication directly contradicts the values and vision of TOH, and those articulated by the Elizabeth and Matthew Policy on Communication and Access.

More than 15 000 people have surgery at TOH every year, and many suffer complications. However, most patients are not informed of their personalized risks, despite this being a requirement of informed consent. Patients want more information about their risks and expected recovery from surgery, and lack of timely and effective communication of this information is not in keeping with TOH's vision and values. Therefore, our specific objectives are to: (1) develop a patient-oriented, personalized preoperative risk communication tablet application; and (2) to evaluate whether the application improves patient knowledge of their personalized risk profile, and satisfaction with their perioperative care.

Our own research on provision of individualized preoperative risk (documented for less than 1 in 5 patients)¹ is consistent with the existing literature.^{2,3} Additionally, a lack of communication of possible risks of surgery is the leading complaint in post-surgery medicolegal cases.⁴ Several studies demonstrate that patients feel that the information that they receive before surgery is insufficient, and that this is not adequately addressed by clinicians.^{2,3,5} Furthermore, despite discussion of risks being potentially anxiety provoking, better informed patients tend to have less preoperative anxiety and be more satisfied.⁶ We have completed a scoping review, which screened over 700 papers using a peer-reviewed, structured search strategy. We identified only 2 processes to communicate personalized risk to patients none that used technology, and none that had undergone evaluation of their effectiveness. Therefore, our proposed process and tablet application represent a novel intervention to address a key gap in perioperative patient-centered care.

We have evidence from our own preoperative clinics that patients can provide their personal health data with a high degree of accuracy (moderate to excellent agreement with physician health histories for all health conditions included in the NSQIP risk calculator).⁷ And when applied to our TOH patients, the NSQIP risk calculator shows high levels of predictive accuracy (c-statistic >0.9 for mortality, >0.8 for serious complications and LOS; excellent calibration (Hosmer-Lemeshow p>0.05 for all outcomes; overall accuracy Brier score <0.1). Finally, systematic reviews demonstrate that when risk prediction tools and clinical information technology are integrated into care processes in a manner that leverages accurate, local data while engaging and involving patients, the likelihood of successful implementation is increased substantially.^{8,9}

[name] – Research Proposal

A Patient-oriented risk communication tool to improve patient experience, knowledge and outcomes after elective surgery

Methods

In collaboration with the TOH mHealth team we are developing a tablet-based, patient-oriented, personalized risk communication application. The application leverages features of inclusive design, meaning that it will be useable even by older patients, who represent the largest demographic of surgical patients at TOH. Older individuals are often less tech-familiar, and may have visual and motor challenges that can make mobile technology use difficult. The application features simple and consistent design, large well-lit buttons that tolerate tremor, and simple language. The process will be applied in preoperative clinics at TOH, where patients will be asked to provide their personal health history through a series of questions already used on our TOH preoperative health screener. These values will then populate the NSQIP Universal Risk Calculator, which we have calibrated to TOH data, to generate personalized risks of mortality, serious complications, and hospital length of stay. These risk estimates will be communicated directly to the patient using absolute risk estimates represented pictorially (best practice for risk communication to patients). Risk estimates will also be provided to the patient's clinician. To facilitate shared discussion between patients and physicians, we will also ask the patient to identify up to 3 benefits they hope to achieve from surgery, and patients and clinicians will be provided with 3 evidence-based questions known to support Shared Decision Making (What are my options? What are the pros and cons of each option? How do I get the support to make the right decision for me?).

Study Design

The application will be evaluated using a controlled before-after study design. Patients will be recruited using standardized procedures, and process and outcome measures will be recorded using the same tools and methods in both study phases to decrease the risk of measurement and selection bias. The knowledge questionnaire will be completed prior to the clinic appointment, and repeated after. The primary outcome measure will be the change in knowledge from prior to the clinic appointment to after comparing the pre- and post-implementation groups. The satisfaction (patient experience) questionnaire will be administered after each patient's clinic appointment.

Outcomes

Primary outcome: The primary outcome will be the change in patient knowledge of their risk profile from before their PAU appointment to after. A knowledge questionnaire has been developed using recommended standards.¹⁰ The questionnaire will not test perceived knowledge, but will test factual items specifically related to the patient's personalized risk profile.¹¹ The pre- and post-appointment knowledge scores will be normalized on a 100 point scale [(questions correct/total questions)*100].

Secondary patient-centered outcomes: Patient experience will be assessed using a likelihood to recommend measurement based on a 10-point Likert scale as recommended by the Institute for Healthcare Improvement's Triple Aim measurement guide.¹² The value of the intervention will be defined using a patient-perceived equation as proposed by Morgan et al.¹³ This value framework derives patient-value by dividing patient outcomes measured in natural units by total costs that borne to patients. We will also use a micro-costing technique¹⁴ to estimate the total costs of the eHealth application that covers the costs of iPads, application development and training. Patient anxiety levels

[name] – Research Proposal

A Patient-oriented risk communication tool to improve patient experience, knowledge and outcomes after elective surgery

will be measured using the Short Form State-Trait Anxiety Inventory,¹⁵ and acceptability will be measured using a modified version of a validated 5-point Likert scale.¹⁶

Secondary clinician-centered outcomes: Likelihood to change management will be measured using a 5-point scale, acceptability will be measured using a 5-point Likert scale.¹⁶

Feasibility outcomes: Proportion of patients for whom a risk score can be calculated, proportion of missing data from patient-entered health questionnaire, proportion of patients with an expected length of stay $\geq 75^{\text{th}}$ procedure specific percentile where notification of expected prolonged length of stay is sent to the most responsible physician.

System outcomes: Hospital length of stay in patients with an expected length of stay greater than the 75th procedure specific percentile (captured from linkage to hospital administrative data; the 75th percentile is the most commonly used cut off to define prolonged LOS).^{17,18}

Study population: We will recruit all consenting adults aged 18 or older seen in the Pre-Admission Unit prior to elective inpatient surgery at The Ottawa Hospital. Participants will be excluded if they are unable to communicate in English or French, or if they are unable to provide consent on their own due to cognitive impairment. Those scheduled for gastric bypass surgery will also be excluded due to significant differences in their pre-operative risk discussion.

During the post-implementation phase, patients will only be invited to participate in the study if the physician in clinic has provided consent for the study.

Sample Size: Sample sizes of 86 patients before and 86 after achieves 90% power to detect a minimally important difference in the mean improvement in knowledge test of 5 points (i.e., an improvement of 10 points after implementation versus 5 points before implementation) assuming a standard deviation for both groups of 10 and using a two-sided two-sample equal variance t-test at the 5% level of significance. 95 per group will allow for 10% dropout.

Data collection and management: Baseline and outcome data will be measured using various questionnaires (see study flow). Responses will be captured and stored via a RedCap data collection interface on a secure institutional research server. Length of stay data will be obtained by linking our data to our hospital Data Warehouse. All data will be stored in a privacy legislation-compliant manner.

Statistical analysis: Descriptive statistics will be used to compare recruitment rates and characteristics of patients in the pre- and post-implementation phases. Two-sample t-tests or chi-squared tests, as appropriate, will be used to examine statistical significance of differences. All outcomes will be expressed as biweekly means with graphical interpretation as a first step, using biweekly time series plots to detect the presence of any immediate versus gradual effects of intervention, and to examine the presence of trends, cyclical patterns, and outliers.

Primary outcome (change in knowledge from before to after PAU appointment) will be analyzed using a linear segmented regression analysis of the biweekly means. The presence of autocorrelation will be assessed using Durbin-Watson tests, as well as visual inspection of residual plots. If autocorrelation is present, an autocorrelation parameter will be included in the model. The effect of the intervention will be reported as level and trend changes after the intervention, together with 95% confidence intervals. Patient-level linear regression analysis will be additionally conducted to adjust for potential differences

[name] – Research Proposal

A Patient-oriented risk communication tool to improve patient experience, knowledge and outcomes after elective surgery

[figure not shown]
in patient characteristics from pre- to post-implementation and to examine any predictors of outcomes or subgroup effects (e.g., by patient age, sex, multimorbidity status, and procedure). Subgroup analyses will be conducted by including the subgroup variables as well as their interaction with the intervention indicator into the regression models. All analyses will be conducted using SAS v. 9.4 with $\alpha = 0.05$ set for statistical significance.

Secondary patient-centered outcomes (patient experience, value, anxiety, acceptability) will be analyzed as described for the primary outcome. Normalizing transformations will be considered for patient-level analyses in case of substantial skewness, while ordinal logistic regression will be used for outcomes measured using a 5 point Likert scale.

Clinician-centered outcomes (likelihood to change management and acceptability, both measured using a 5-point scale) will be analyzed using biweekly summary measures using segmented autoregression as described for the primary outcome.

Feasibility and system outcomes will be described using frequencies and proportions and tabulated overall, and by implementation phase. Hospital length of stay will be analyzed using segmented linear regression as described for the primary outcome.

Study Flow: Questionnaires

[name] – Research Proposal

A Patient-oriented risk communication tool to improve patient experience, knowledge and outcomes after elective surgery

References

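### Patient value is outcome divided by patient-borne cost, analysed like the primary outcome; the per-patient ratio is undefined at zero cost, dominated by small costs, and mis-ranks negative outcomes

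*Combined protocol and SAP*

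**What the plan says.** Under Outcomes (secondary patient-centered outcomes), the combined protocol and SAP takes its definition of value from a cited framework: "This value framework derives patient-value by dividing patient outcomes measured in natural units by total costs that borne to patients". The text does not say which outcome is the numerator, which patient costs count, or whether the ratio is formed per patient or from group totals. A separate micro-costing exercise is planned "to estimate the total costs of the eHealth application that covers the costs of iPads, application development and training". That is the cost of the application, not the patient-borne denominator.

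Under Statistical analysis, value is named among the outcomes that follow the primary analysis: "Secondary patient-centered outcomes (patient experience, value, anxiety, acceptability) will be analyzed as described for the primary outcome". The primary outcome "will be analyzed using a linear segmented regression analysis of the biweekly means", and "Patient-level linear regression analysis will be additionally conducted to adjust for potential differences" in patient characteristics between phases, with subgroup interactions. The one distributional safeguard is this: "Normalizing transformations will be considered for patient-level analyses in case of substantial skewness". No rule covers zero cost, very small cost, or a zero or negative outcome.

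**The concern.** The definition alone leaves room for a group-level ratio. The analysis section does not, because a patient-level regression with covariates needs one value per patient. A biweekly mean could in principle be a ratio of period means, but the plan does not say so, and a mean of patient ratios inherits every defect of the ratios.

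Three defects follow. A patient who bears no cost, the most favourable case on the cost side, has no value and must be dropped or handled ad hoc. A patient with a tiny cost can outweigh many others. If the numerator can be negative, a higher cost pulls the ratio towards zero and so reads as better value.

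The skewness provision repairs none of this. No transformation defines division by zero, and a log cannot take non-positive values. The provision is also limited to patient-level analyses, so the main biweekly-mean analysis has no protection. At stake is whether the value result is interpretable, and whether choices about zero-cost and extreme patients are made after the data are seen.

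**Working it through.** **Plan's own figure.** The Sample Size paragraph states "Sample sizes of 86 patients before and 86 after achieves 90% power", for "an improvement of 10 points after implementation versus 5 points before implementation", SD 10, two-sided 5% t-test. The noncentral t gives 89.99% power at 85 per phase and 90.3% at 86, so 86 reproduces. It applies to knowledge change only; the plan gives no figure for value.

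**Zero cost.** The zero-cost share is not in the documents. For assumed shares of 1%, 5% and 20% among 2 × 86 = 172 patients:
- expected patients without a value: 172 × 0.01 = 1.7, 172 × 0.05 = 8.6, 172 × 0.20 = 34.4;
- chance of at least one: 1 − 0.99^172 = 82% at a 1% share, and above 99.9% at 5%;
- chance that a biweekly mean of 8 patients (assumed) is undefined: 1 − 0.99^8 = 8%, 1 − 0.95^8 = 34%, 1 − 0.80^8 = 83%.

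**Small cost.** A 10-point gain scores 10/100 = 0.1, 10/50 = 0.2 or 10/1 = 10. In simulation with cost uniform on 1 to 100 (assumed), the 9 most extreme of 172 patients carry a median 87% of the within-group sum of squares, against 28% for the outcome alone.

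**Negative outcome.** A change of −10 gives −10/10 = −1.0 at cost 10 and −10/100 = −0.1 at cost 100, so the costlier patient ranks higher. A change of 0 gives 0 at any cost. If knowledge change is the numerator (assumed), the plan's means and SD give P(change ≤ 0) = Φ(−5/10) = 30.9% before and Φ(−10/10) = 15.9% after, about 27 and 14 of 86. These shares include zeros, for which cost is ignored rather than reversed. With an assumed 10-item test, so that scores move in steps of 10, strictly negative changes are about Φ((−5 − 5)/10) = 16% and Φ((−5 − 10)/10) = 7%.

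**Power, knowledge change as numerator.** Assumptions: lognormal cost, no zeros, unrelated to outcome or phase. Let k = CV² of cost; for a lognormal, 1/cost has the same CV.
- Per-patient ratio, in units of E(1/cost): difference 5, variance (σ² + μ²)(1 + k) − μ² in each phase.
- Ratio of means, in units of 1/mean cost: difference 5, variance approximately σ² + kμ².

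At CV 0.6, k = 0.36:
- per patient: 125 × 1.36 − 25 = 145 and 200 × 1.36 − 100 = 172; SE = √(317/86) = 1.92; 5/1.92 = 2.60; power ≈ Φ(2.60 − 1.96) = 74%;
- ratio of means: 100 + 9 = 109 and 100 + 36 = 136; SE = √(245/86) = 1.69; 5/1.69 = 2.96; power ≈ Φ(2.96 − 1.96) = 84%.

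Simulation (86 per phase; t-test on ratios against a delta-method test on the ratio of means) agrees:

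| Cost CV | Per-patient ratio | Ratio of means |
|---|---|---|
| 0.3 | 87% | 89% |
| 0.6 | 75% | 84% |
| 1.0 | 57% | 74% |
| 1.5 | 41% | 61% |

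Knowledge change analysed without any cost has about 90% power.

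**Power, positive numerator.** With recommend scores of mean 7 and 8, SD 2, clipped to 1–10 (all assumed) and the same costs, a log per-patient ratio gives 58%, 29%, 18% and 13%, against 53%, 24%, 14% and 11% for the ratio of means.

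**Direction.** With cost unrelated to outcome or phase, the expected phase difference in the mean ratio is 5 × E(1/cost), which always has the right sign. With the knowledge numerator, significant results in the wrong direction occurred in at most 1 of 10,000 runs at any of these CVs. Wrong-sign point estimates were about 0.1% at CV 0.3 and 5% at CV 1.5.

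**The case against.** The strongest reply is that every harm needs something the documents do not supply. The cited framework may fix the numerator, the cost items and a zero-cost convention. If total costs include time or travel, zeros may never arise. The value sentences directly follow the likelihood-to-recommend score, which would not normally be non-positive; with that numerator, mis-ranking disappears and the plan's transformation option works slightly better than a ratio of means. No power is claimed for value, much of the loss comes from cost variation that also hurts the ratio of means, and the simulation is a t-test rather than segmented regression. Finally, in a non-randomised before-after study, giving up covariate and trend adjustment would be a real loss.

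Most of this stands as a limit on size. It does not remove the defect: the plan must work on its own text, which neither names a numerator nor excludes zero or small costs, and positive costs can still be small. The point about adjustment stands in full, and the fix below keeps it.

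A reader might also infer that the ratio could make the worse phase look better. The documents do not support that. Mis-ranking of individual patients is not a reversed phase comparison, and under the assumptions above a significant reversal practically never occurs. Nor should the power figures be read as a forecast for this trial, since the numerator and the cost distribution are both assumed.

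**Conclusion.** The point holds as a defect in one named secondary outcome and should be corrected before analysis. That the planned analysis needs a ratio per patient, and that this ratio fails at zero cost and is unstable at small cost, follows from the text and arithmetic alone. Mis-ranking is conditional on a numerator that can be negative: possible for knowledge change, not normally for the recommend score.

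The size is conditional too. With knowledge change and the assumed costs, the per-patient ratio gives up about 2 points of power against a ratio of means at cost CV 0.3 (89 − 87) and about 20 at CV 1.5 (61 − 41). With a positive numerator the gap is small and favours a log ratio. The frequency of zero or small costs cannot be judged from the documents. The primary analysis and the sample size are unaffected.

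**What to change.** - Name the numerator and list the patient costs counted.
- Analyse outcome and patient-borne cost as two separate variables, each with the planned segmented model and the planned covariate-adjusted patient-level model. Pre/post adjustment is then kept and zero-cost patients stay in.
- Report value per phase as adjusted mean outcome divided by adjusted mean patient cost, with a patient-level bootstrap 95% confidence interval for the between-phase difference. Show both means beside it, because a ratio of means still misreads cost if a phase mean outcome is negative.
- Remove value itself from the biweekly-mean and patient-level regression analyses.

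The cost is some SAP wording and a short bootstrap program. Value becomes a phase-level rather than a patient-level quantity, so it has no biweekly plot or subgroup regression of its own; its two components keep theirs.

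### Physician consent limits who is invited in the post-implementation phase only, so a difference in usual-care knowledge gain between consenting and declining physicians would mix with the estimated intervention effect

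*Combined protocol and SAP*

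**What the plan says.** The Study population section opens with one rule for the whole study: "We will recruit all consenting adults aged 18 or older seen in the Pre-Admission Unit". It then adds a condition for one phase: "During the post-implementation phase, patients will only be invited to participate in the study if the physician in clinic has provided consent". The Study Design section offers common procedures as the protection against selection: "Patients will be recruited using standardized procedures", with measurement by the same tools "in both study phases to decrease the risk of measurement and selection bias". The design is called controlled, but only pre- and post-implementation groups are described, with no concurrent comparison group.

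The Statistical analysis section fits a segmented regression to biweekly means of the knowledge change. On reporting it says: "The effect of the intervention will be reported as level and trend changes after the intervention". Two other provisions bear on the point. The first is descriptive: "Descriptive statistics will be used to compare recruitment rates and characteristics of patients in the pre- and post-implementation phases". The second is a patient-level regression that adjusts for patient characteristics and looks at predictors, with age, sex, multimorbidity and procedure as examples. No analysis names the physician.

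**The concern.** The primary outcome is knowledge gained across a clinic visit, and the physician who conducts the visit is a plausible source of that gain. Under the plan as written, patients of physicians who later decline can be in the pre-phase but not in the post-phase. The change in who is eligible starts together with the application. If usual-care gain differs by physician consent status, the pre-post contrast combines that difference with the effect of the application.

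The planned safeguards help only partly. Recruitment rates by phase might hint at a narrower pool, but their denominator is not defined and they do not identify physicians. Adjustment for patient characteristics removes only the part of a physician difference that runs through case mix or procedure. The open-ended wording on predictors allows a physician term without committing to one, and biweekly means carry no physician information.

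**Working it through.** **Inputs from the Sample Size section.** 86 per phase, difference 5 points, SD 10, two-sided 5% test, 90% power. **Assumed, because the documents do not give them:** q, the share of pre-phase patients seen by physicians who later consent (0.8 or 0.5); the physician intraclass correlation, ICC (0.02 to 0.10); 6 or 12 biweekly points per phase. The target is taken as the effect among patients of consenting physicians; the plan does not state one.

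**1. The plan's own figure.** The exact noncentral-t power is 89.99% at 85 per group and 90.3% at 86, so 86 per group reproduces.

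**2. The bias.** Let Gc and Gd be the mean usual-care gains with consenting and declining physicians, and D = Gc - Gd. The pre-phase mean is q x Gc + (1-q) x Gd. The post-phase mean, if the application does nothing, is Gc. The difference is (1-q) x D. It is zero if q = 1 or D = 0.

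**3. An upper bound.** The variance explained by consent status, q(1-q)D², cannot exceed the between-physician variance, ICC x 10². Hence the absolute bias is at most 10 x sqrt(ICC x (1-q)/q).

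| ICC | q = 0.8 | q = 0.5 |
|---|---|---|
| 0.02 | 10 x sqrt(0.005) = 0.71 | 10 x sqrt(0.02) = 1.41 |
| 0.05 | 10 x sqrt(0.0125) = 1.12 | 10 x sqrt(0.05) = 2.24 |
| 0.10 | 10 x sqrt(0.025) = 1.58 | 10 x sqrt(0.10) = 3.16 |

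These are ceilings, reached only if consent status explains all between-physician variation. If it explains half, multiply by sqrt(0.5) = 0.71: 0.5 to 1.1 points at q = 0.8 and 1.0 to 2.2 at q = 0.5. If consent is unrelated to gain, with 10 or 20 equal-sized physician groups assumed, the bias averages zero, with an SD of 0.2 to 0.5 (q = 0.8) or 0.3 to 1.0 (q = 0.5).

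**4. Where it appears.** The segmented model has an intercept, time, level change and trend change. A constant 2-point step at the start of the post-phase returns a level change of 2.0 and a trend change of 0. If the 2-point distortion fades linearly to zero over the post-phase, as it might if consent accrues, the level change is still 2.0, with a trend change of -0.4 per period (6 points) or -0.18 (12 points).

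**5. Rejection rate with no true effect.** The segmented model (86 patients per phase spread evenly, independent errors) has a level-change SE of 3.11 with 6 points and 3.07 with 12. The planning t-test has SE 10 x sqrt(2/86) = 1.52.

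| Bias (points) | Segmented model, 6 / 12 points | t-test, 86 per group |
|---|---|---|
| 0.7 | 5.5% / 5.5% | 7.4% |
| 1.6 | 7.4% / 7.9% | 18% |
| 3.2 | 14.9% / 16.9% | 54% (at 3.16) |

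A patient-level regression without time terms would behave much like the t-test.

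**6. Precision after restriction.** Restricting the pre-phase leaves about 0.8 x 86 = 69 or 0.5 x 86 = 43 patients, against 86 post-phase. The SE, 10 x sqrt(1/n + 1/86), is 1.62 or 1.87. The t-test power for 5 points is 86.7% or 75.7%. In the segmented model, power for 5 points is 29-34% with all patients, 26-31% at q = 0.8 and 20-25% at q = 0.5.

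**The case against.** The strongest reply is that the harm needs two things that the documents do not establish: that some physicians decline, and that usual-care gain differs by consent status. Every bias figure above rests on assumed q and ICC. In the milder case (q = 0.8, consent explaining half the variation) the bound is 0.5 to 1.1 points, small beside a segmented-model SE of about 3.1. This stands, and it limits the point to a cheap improvement.

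Post-phase consent also has a plausible reason: clinicians receive the risk estimates and supply outcomes of their own. Asking physicians before the pre-phase could itself change usual care. A reader might infer that the eligibility rule is wrong; the documents do not support that. What is missing is a way to check its consequence.

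Some cover may exist that the text does not show. The study-flow figure is not available here. The plan also analyses clinician outcomes by the same segmented method, which taken literally needs pre-phase clinician data. The Data Warehouse linkage might allow the physician to be identified later. A reader might therefore go too far in inferring that the bias could never be examined without a new field. None of these sources is stated to hold a physician identifier, however, so the request remains.

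Finally, the tablet gives its output to the patient: "These risk estimates will be communicated directly to the patient using absolute risk estimates represented pictorially". For a clinic-wide target, the bias is (1-q) times the difference in gain under the application, which could be smaller for that reason. The documents do not say.

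**Conclusion.** The asymmetry is written into the plan; its effect is conditional. If some physicians decline and usual-care gain differs by consent status, the difference is mixed with the intervention effect. It enters the level change if the consenting set is fixed from the start of the post-phase, and partly the trend change if consent accrues. Against a 5-point minimally important difference, the assumed inputs bound it at 0.7 to 1.6 points (q = 0.8) or 1.4 to 3.2 points (q = 0.5), in an unknown direction.

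Three stronger readings should be resisted. One is that the result will be biased: the documents give no refusal rate or physician variation, and zero remains possible. Another is that the bias must fall wholly in the level change: the text says only that the physician has consented, not when. The third is that only the point estimate suffers and not the false-positive rate: that fits only the low-powered segmented model, since the t-test rate could reach 54% at the most extreme bound.

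This is a cheap improvement worth making, held with medium confidence.

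**What to change.** Record a physician code for every patient in both phases, if it is not already captured, and report the numbers of physicians approached, consenting and declining. Leave the all-patient primary analysis unchanged. Pre-specify one sensitivity analysis restricted, in both phases, to patients of consenting physicians, or a patient-level model with physician as a fixed effect. State that it estimates the effect among consenting physicians' patients and need not give the clinic-wide effect.

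A random physician effect fitted to all patients is not a substitute. In simulation (86 per phase, 10 or 20 physicians, ICC 0.10, q = 0.5, consent explaining all between-physician variation) it left 2.0 to 2.5 of a 3.0-point bias, while the fixed effect or restriction left about none.

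The cost is one data field, a refusal log, some SAP wording, and lower precision in the sensitivity analysis only. The 86.7% and 75.7% power figures assume no time terms. With them, precision is close to that of the segmented model and power is much lower. The report should therefore say that finding no difference between the two analyses does not prove the absence of bias.
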